4.2 Exclusion Criteria for Light Phenotyping

- History of discitis osteomyelitis (spine infection) or spine tumor
- History of an autoimmune disorder such as ankylosing spondylitis, rheumatoid arthritis, polymyalgia rheumatica, psoriatic arthritis, or lupus
- History of cauda equina syndrome or spinal radiculopathy with functional motor deficit (strength $<4/5$ on manual motor testing)

- History of schizophrenia or schizoaffective diagnosis
- Diagnosis of any vertebral fracture in the last 6 months
- Osteoporosis requiring treatment other than vitamin D and calcium supplements
- Cancer
 - History of any bone-related cancer or cancer that metastasized to the bone
 - Currently in treatment for any cancer or plan to start cancer treatment in the next 12 months
 - History of any cancer treatment in the last 24 months
- Life expectancy less than 2 years
- Unable to speak and write English
- Visual or hearing difficulties that would preclude participation
- Uncontrolled drug/alcohol addiction
- Individuals started receiving disability or compensation within the past year, or currently involved in litigation
- Pregnancy or breastfeeding
- Individuals on high doses of opioids (over 100 OME per day)
- Scheduled back surgery, back surgery within the last year, or more than one back surgery in the past.
- Expecting to receive an injection of surgical procedure within the next year for their cLBP
- Current/planned (in the next 2 years) enrollment in another study of a device or investigational drug that would interfere with this study, this may include participation in a blinded trial.
- Any other diseases or conditions that would make a patient unsuitable for study participation as determined by the site principal investigators. This would include but not be limited to severe psychiatric disorders, active suicidal ideations or history of suicide attempts, and an uncontrolled drug and/or alcohol addiction)

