6.2 Clinical Data and Medical History

At every visit medical history will be collected and reviewed from the participant. Medications (especially analgesics including opioids), medical diagnoses, family history, surgical history and other treatments reported will be confirmed via EMR review. At every in-person assessment visit, clinical data will be collected on each participant including weight and height, waist and hip ratio, blood pressure, heart rate, temperature, and pregnancy status (urine pregnancy test if potentially pregnant [premenopausal, ambiguous last menstrual period, intact reproductive system]). Comorbidities will be assessed using the Charlson Comorbidity Index (CCI) and EMR review. If the visit is conducted virtually, clinical data such as blood pressure, will be collected from their most recent in person visit.

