9.4 Duloxetine

All study activities for this arm will take place at the Back & Pain Center, Department of Anesthesiology, at the Burlington Building in Ann Arbor or on a HIPAA compliant virtual platform like Zoom. Participants randomized

Figure 7 Sample MeTime Acupressure App

[figure not shown]

Figure 8 Location of Acupressure Points

to the duloxetine arm will review the dosing schedule for the medication and safety information for the medication at the pre-intervention visit (T2 for Treatment 1 or T3 for Treatment 2) with the study coordinator. At the baseline visits a physical exam was performed by a physician and drug contraindications will be reviewed as an additional precautionary measure.

Participants will then be given 105 pills of 30mg duloxetine with an 8-week dose escalation schedule and an additional 11 pills for those who would like to taper. Participants will be asked to start taking the medication from home, 7 days after the pre-intervention visit (T2/T3 visit). In the event of a shutdown due to COVID, participants may be mailed the study medications by the research pharmacy.

The first day of the medication will be day 1 and subjects will be scheduled for a phone visit with the study team at day 7 and day 42 (or the next business day if this falls on a weekend). A check in call will be made by the study team 48 hours after starting the treatment to address any patient questions or concerns. For days 1-7, patients will take 30mg of duloxetine once a day, in the morning. Starting day 8, participants tolerating the medication will be escalated to 60mg once a day. They will also have the option of staying at 30mg, once a day or stopping the medication (see Figure 9 below).

Participants will be scheduled for a phone visit with the study team at the end of week 1 to discuss dose escalation and at the end of week 6 to discuss dose taper. At the end of the 8-week intervention period, participants will have the option to continue the medication commercially (non-study medication) under the care of their physician or taper off the medication. During the entire 8-week intervention, patients will be asked to keep a daily log of medication dosage, any missed doses, and any side-effects they may have experienced.

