Potential Risk – Treatment Interaction – Acupressure. Self-acupressure is a safe intervention. From our previous 3 clinical trials over the past 10 years using this acupressure point formula, we have observed no serious adverse events associated with the study intervention. Our most recent and largest trial of self-acupressure in fatigued cancer survivors (N=288),⁶³ had 6 adverse events related to acupressure, and all were non-serious cases of mild bruising at acupressure sites. There are no known long-term risks associated with self-acupressure. To minimize the chances of bruising, participants will be trained by the acupressure instructor in how to apply the correct amount of pressure with the AcuWand. Specific attention will be paid to not apply too much pressure. The AcuWand has a built in “buzzer” to notify the study participant when the correct amount of pressure is reached, which will minimize chances of bruising. Phone calls will also be made to the participants for the first 2 weeks of self-acupressure by the study coordinator to monitor progress and answer questions. The participant is free to withdraw from the intervention at any point if the self-acupressure intervention becomes uncomfortable.

Potential Risk – Duloxetine. Duloxetine will also be administered as it typically would be by an experienced provider, again focusing on slow gradual dose escalation. Participants will be warned about the most common

side effects with this drug include nausea, vomiting, nausea, dry mouth, constipation, diarrhea, fatigue, difficulty sleeping, dizziness, light-headedness, mood swings, sexual dysfunction, and rarely, allergic reaction. All of these side effects are thought to be less common with slow gradual dose escalation, and many (especially gastrointestinal intolerance) typically get better over time. The most serious adverse effect associated with duloxetine, and one which causes us to modify our exclusion criteria for the entire study, is the increased risk of suicidality with initiation of this drug, especially in individuals under age 25. Thus, we exclude individuals under age 25 or with a history or active suicidality from participating in our MRC study. Additionally, duloxetine is a category C medication with unknown risk to fetus. Participants will be advised of this and will be asked to either abstain from sexual activities or use an acceptable method of birth control.

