#### **5.4.3 Exclusion Criteria for Light Phenotyping**

- History of discitis osteomyelitis (spine infection) or spine tumor
- History of ankylosing spondylitis, rheumatoid arthritis, polymyalgia rheumatica, psoriatic arthritis, or lupus
- History of cauda equina syndrome or spinal radiculopathy with functional motor deficit (strength  $<4/5$  on manual motor testing)
- History of schizophrenia or schizoaffective diagnosis
- Diagnosis of any vertebral fracture in the last 6 months
- Osteoporosis requiring treatment other than vitamin D and calcium supplements
- Cancer
  - History of any bone-related cancer or cancer that metastasized to the bone
  - Currently in treatment for any cancer or plan to start cancer treatment in the next 12 months
  - History of any cancer treatment in the last 24 months
- Life expectancy less than 2 years
- Unable to speak and write English
- Visual or hearing difficulties that would preclude participation
- Uncontrolled drug/alcohol addiction
- Individuals receiving disability or compensation within the past year, or involved in litigation
- Pregnancy or breastfeeding
- Individuals on high doses of opioids (over 100 OME per day)
- Scheduled back surgery, back surgery within the last year, or more than one back surgery in the past.
- Expecting to receive an injection of surgical procedure within the next year for their cLBP
- Current/planned (in the next 2 years) enrollment in another study of a device or investigational drug that would interfere with this study, this may include participation in a blinded trial.
- Any other diseases or conditions that would make a patient unsuitable for study participation as determined by the site principal investigators. This would include but not be

limited to severe psychiatric disorders, active suicidal ideations or history of suicide attempts, and an uncontrolled drug and/or alcohol addiction.

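### Duloxetine is first taken about 6 or 15 weeks after T1, and no listed item requires staff to ask about current suicidal ideation before it is assigned

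*Protocol*

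**What the plan says.** Protocol 19.1 ties suicidality to starting duloxetine and ranks it this way: "The most serious adverse effect associated with duloxetine, and one which causes us to modify our exclusion criteria for the entire study". The control follows directly: "Thus, we exclude individuals under age 25 or with a history or active suicidality from participating in our MRC study".

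The age half of that control is firm: Protocol section 4 and SAP 5.4.1 set 25 to 70 years. The suicidality half sits in the last bullet of Protocol 4.2, which covers conditions that make a person "unsuitable for study participation as determined by the site principal investigators" and continues: "This would include but not be limited to severe psychiatric disorders, active suicidal ideations or history of suicide attempts". SAP 5.4.3 repeats it ("active suicidal ideations or history of suicide attempts").

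Treatment is assigned later. Protocol 8.1 places randomisation at T2 and T3, depending on PGIC and on which treatments the person is eligible for. For duloxetine, 9.4 adds a review of dosing and safety information with the study coordinator at that visit, and says that "drug contraindications will be reviewed as an additional precautionary measure". It then states: "Participants will then be given 105 pills of 30mg duloxetine with an 8-week dose escalation schedule". Dosing starts at home 7 days after the visit.

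Other relevant provisions are general history-taking (6.2: "At every visit medical history will be collected and reviewed from the participant"); PROMIS Depression-4 and PHQ-2 in the schedules (Protocol 1.3, SAP Table 1); calls at 48 hours, day 7 and day 42 of treatment (9.4); and a duloxetine block in Table 9 that covers self-harm thoughts and suicidal ideation.

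**The concern.** The protocol links the risk to initiation of the drug, but the control it names operates at entry. A person can be free of ideation at T1 and develop it during the run-in or during the first treatment. As the plan is written, that person can be assigned duloxetine and given the full supply unless they raise the matter or staff choose to ask. This concerns participant safety. It does not affect the primary endpoint or the analysis model.

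**Working it through.** No statistical figure is in dispute. The check is a reading of every listed safeguard between T1 and first dose, with some simple arithmetic.

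**Timing.** Protocol 12.1 puts T1, T2 and T3 at weeks 1, 6 and 15; 9.4 adds 7 days before the first dose.
- Stage 1: 6 + 1 − 1 = 6 weeks from T1 to first dose.
- Stage 2: 15 + 1 − 1 = 15 weeks.
- With the ±2-week visit window in SAP 5.6, the ranges are 4 to 8 and 13 to 17 weeks.

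**What each listed item does.**

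| Item | Place | Does it require asking about current ideation before assignment? |
|---|---|---|
| Randomisation criteria | 8.1 | No: PGIC and treatment eligibility only |
| Duloxetine contraindications | 4.3.1, SAP 5.4.4.1 | No: interacting drugs, renal and hepatic limits, allergy, bipolar disorder |
| Dosing, safety and contraindication review | 9.4 | No: it works from the lists above |
| Medical history at every visit | 6.2 | No: general, suicidality not named |
| PROMIS Depression-4, PHQ-2 | 1.3, SAP Table 1 | No: mood is measured, but no item or score is linked to assignment |
| Schedule of assessments | 1.3, SAP Table 1 | No row is named for suicidality |
| Calls at 48 hours, day 7, day 42 | 9.4 to 9.4.2 | No: after the first dose, and general |
| Adverse event reporting | 23.1.1 | No: relies on the participant to volunteer events |
| Withdrawal when criteria are no longer met | 22.2 | No: permissive, with no scheduled recheck |
| Table 9, duloxetine block | 23.1.5 | No: referral, emergency services and possible discontinuation once ideation is known |

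**Supply.** Eight weeks is 56 days: 7 days at one 30 mg pill plus 49 days at two gives 7 + 98 = 105 pills, matching 9.4. The whole course is dispensed at once.

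**People who pass this point.** SAP 5.4.1 targets 408 randomised.
- Stage 1: 408 / 4 = 102 assigned duloxetine.
- Stage 2: 408 − 102 = 306 in other arms. If all are re-randomised equally and are eligible for all three remaining arms, 306 / 3 = 102; if half are, 153 / 3 = 51.
- Total: 102 (none re-randomised), 153 (half) or 204 (all).
- The protocol's own arm sizes, 100 (section 4) or 110 (section 8), give 100 to 200 or 110 to 220 by the same steps.

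**Comparison within the protocol.** Pregnancy is also an entry exclusion and is raised in the same 19.1 paragraph. Urine testing is repeated, where applicable, at T1 to T5 (6.6; 6.6.3 says T1 to T4). That testing also serves MRI safety, but it shows that an entry criterion can be rechecked at T2 and T3 in this trial.

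**The case against.** The strongest reply is that the check may exist elsewhere. The screening forms, SOPs and DSMP are separate documents, and 19.4 refers to decision flowcharts that name suicidal ideation. A reader might infer that staff will not ask; the documents do not support that. They support only the narrower statement that nothing listed requires the question. If another document already contains it, the protocol need only say so. But a safeguard that has not been seen cannot be assumed.

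It can also be said that mood is measured repeatedly, that 19.1 has duloxetine given by an experienced provider, and that 19.4 offers a route to psychiatric help in every arm. These points are correct as far as they go. The mood scales have no action rule, and the 19.4 route is for distress while completing questionnaires.

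Three stronger readings should be resisted.
- A reader might conclude that the suicidality exclusion is missing or defective in 4.2. It is not: active ideation and past attempts are both named there, and 19.1 may simply be shorthand for that bullet. Its place in an open-ended, investigator-judged list is an editorial matter. If suicidality is meant to be settled for the whole study at entry, its absence from 4.3.1 is also understandable.
- A reader might conclude that ideation in the duloxetine arm would go unmanaged while MBSR participants are protected. Section 19.1 does commit the MBSR therapist to weekly monitoring, and the duloxetine text has no equivalent. But Table 9 provides a response for duloxetine, and part of the difference reflects weekly contact with a therapist against a self-administered drug.
- A reader might take 102 to 204 as people at risk. It is everyone assigned duloxetine.

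**Conclusion.** The point holds in a limited form. The protocol identifies a risk at initiation, controls it by an exclusion at entry, and leaves nominally 6 or 15 weeks before first dose with no listed requirement to ask about current ideation. What exists is general, or acts only after disclosure. On the SAP's target, between 102 and about 204 people pass through this gap; the upper figure assumes that everyone in the other arms is re-randomised equally and is eligible for every remaining arm. The documents give no rate of new ideation, so the number affected cannot be estimated and no harm is demonstrated. The conclusion rests on the protocol and SAP alone. The change is worth making because the harm is the one the protocol itself ranks highest for this drug and the remedy is small.

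**What to change.** Add one documented question on current suicidal ideation at T2 and T3, answered and reviewed before randomisation, including when the visit is virtual. List a positive answer as making the person ineligible for duloxetine in Protocol 4.3.1 and SAP 5.4.4.1. It should also trigger evaluation by a study clinician and a decision under 4.2 and 22.2 on continued participation. Randomisation should wait for that decision rather than move the person automatically to another arm, because 19.1 lists worsening of psychiatric symptoms as a risk of MBSR too.

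The question goes to about 408 people at T2 and at most 408 at T3, at visits that already take place, and needs a short amendment to both documents. The real cost is that a study clinician must be reachable for the few positive answers, including at virtual visits. A few more people will become ineligible; someone already barred from another arm would fall below the three-treatment minimum in 4.1.

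Aligning the wording of 4.2 and SAP 5.4.3 with 19.1 is optional and editorial.

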19.2 Potential Risks Associated with Deep Phenotyping

Potential Risk – Quantitative Sensory Testing (QST) Pressure delivery devices, including the MAST stimulator, manual algometer, pinprick, and rapid cuff inflator (used before and during MRI) may result in temporary discomfort and areas of skin indentation and/or reddening that resolves within minutes to a couple hours. These risks are deemed to be "common" but not serious to the patient. Although uncommon, some participants have reported mild tissue/muscle tenderness lasting for up to one day following testing. In rare cases, minor bruising has been reported following pressure stimulation. This resolves in a few days. The two-point discrimination aesthesiometer, the cold water used for CPM, and the M-VAST visual stimulus may also result in transient discomfort that usually resolves in a few seconds to a couple minutes after the test stops. Additional possible discomfort of the visual stimulation task may be headache or nausea while or after performing this task.

Potential Risk - MRI. Described in Section 19.1.

Potential Risk - Back Maneuvers (performed before and during MRI). Patients will undergo a series of exercise maneuvers designed to temporarily increase their low back pain. Previous studies have determined that this increase is on average 34% above baseline and that the duration of exacerbation is less than one hour. However, while no adverse events related to this pain exacerbation have been previously reported, there remains a chance that this pain provocation will last more than one hour.

Potential Risk – Autonomic Nervous System Monitoring (BIOPAC system). The BIOPAC System used for ANS monitoring is non-invasive and MRI-compatible. ECG and respiratory signals will be acquired with two transcutaneous leads (i.e., electrodes) placed above and below the heart and a pneumatic belt placed just below the rib cage. GSR, PPG and temperature will be acquired transcutaneous leads placed on the fingertips of the index and middle fingers. Skin irritation may occur due to skin cleaning and prep (e.g., with alcohol pads), conductive gel, adhesives and materials utilized to affix leads to the subject's skin; however, we anticipate this will rarely occur. We also do not anticipate that any sensations will occur from the recordings. Risks associated with these measures are minimal since they are non-invasive. However, some participants

may experience anxiety and/or a general unease associated with unfamiliar physiological testing and/or when applying or removing sensors

19.3 Adequacy of Protection Against Risks

All patients enrolled in this study will complete an informed consent document which will be approved by the University of Michigan IRBMED. The informed consent interview is conducted by the study staff and includes a verbal and written explanation of the study, including the purpose, testing procedures, time commitment, inclusion/exclusion criteria, risks and benefits, alternative treatments, confidentiality, compensation, study personnel contacts, use of genetic material for research, and required regulatory information. All individuals are given the opportunity to ask questions. Once all questions and concerns are addressed to the participant's satisfaction, the participant signs the consent form.

During the process of obtaining informed consent, participants will be reminded that their responses to questionnaires are confidential and that they may refuse to participate in the project and/or withdraw at any time without any penalty or loss of benefits. All study staff will have completed and passed certification in the proper and ethical handling of consent and participation in human research (e.g., CITI training) to further ensure the proper treatment of individuals participating in this study. The signed informed consent document is stored securely and separately from all other research materials.

19.4 Protections Against Risks

Breach of confidentiality. Several measures have been taken to reduce the risk of breach of confidentiality. These include training of study team members, electronic and physical security measures for data capture and storage, and collecting a minimum of identifiable information for each individual. The study team will take all possible steps to protect the privacy of subjects. This includes:

1. After processing by the biorepository, samples will not be labeled with the subject's name or other easily identified numbers (like social security numbers or date of birth)
2. Subject's samples will be coded (assigned a unique study ID number) which will allow the researchers to link the sample to other information such as questionnaires and other study data.

Discomfort Associated with Assessment Questionnaires. Any participant becoming distressed while completing questionnaires will be encouraged to seek clarification from the local study staff or if any questions are unclear or troubling. All participants are told that they have the option to terminate participation without penalty and/or will be assisted in arranging medical/ psychiatric help including, if necessary, emergency treatment. Staff will have emergency contact procedures in place (established SOPs) should this type of assistance be needed.

Discomfort Associated with EMA and Pro-Diary. Risks associated with EMAs and Pro-diary will be minimized by allowing participants to initiate the wake- and bed-time assessments when it is convenient for them and by allowing participants to opt-out of or postpone EMAs that are not convenient for them (they will be shown how to silence the monitor/delay reporting). These risks will also be minimized by keeping the assessments as brief as possible. Participants may also experience discomfort from wearing the PRO-Diary, especially if they are not used to wearing a watch on a daily basis. This risk is extremely rare in our experience collecting data. We will minimize this risk by offering participants choices of wrist band types and by telling them that it may take a few days to get used to wearing the PRO-Diary.

Discomfort Associated with the non-pharmacological interventions. Participants may withdraw from the study at any time and this will in no way affect their medical care. In the rare event that an adverse event (AE) occurs associated with the conduct of the interventions, the local study staff will be available to assist participants. Study staff will also be trained in how to reach medical care within each clinical site should additional care be needed. There are established protocols for study staff including flowcharts for decision making and addressing various AEs such as an adverse response to the intervention (e.g., worsening pain) or the disclosure of serious psychiatric symptoms (e.g., suicidal ideation, psychotic episode). The PIs and study

coordinators will ensure appropriate follow-up to any AE and the event will be reported in accordance with the UM IRBMED.

Discomfort Associated with Physical Therapy. Participants will be asked to report to the treating therapist about what is causing pain or fatigue and can stop as needed. Participants will be given instructions in symptom relief following treatment such as using an ice pack. They will also be asked to report any pain increase lasting more than 2 hours to the treating therapist at the next visit. The PT program is designed to facilitate movement and to not exacerbate the condition, but all reports of higher symptoms will be discussed to determine if any modifications need to be made.

Blood Draw: The amount of blood collected from participants is limited, consistent with the guidelines established by the University of Michigan IRBMED (i.e., 15cc's). Collection is done in a sterile manner to decrease the risk of infection and performed by trained medical personnel who will apply pressure to the withdrawal site to prevent the possible development of a hematoma. Study team will also be trained to address any patients with vasovagal symptoms.

Laboratory Samples and Inflammatory Marker Analysis: Samples will be stored in a de-identified manner and linked to other phenotyping data only by anonymous subject ID number. Patients are informed during the informed consent process that they will not be offered the results of any laboratory testing as all analyses will be performed on an anonymous dataset.

MRI. To minimize the risk from the MRI, participants will complete and sign a safety screening form provided by the University of Michigan and will be instructed to bring or wear clothing without metal fasteners, and remove jewelry and any other metal objects from their body. All people (including staff) who enter the exam room that contains the magnet are hand screened for magnetic material before entering. Also, participants will wear foam earplugs or headphones to reduce the loud noises made by the scanner. Participants will be able to communicate with the examiner throughout the scan. If needed, the participant will be removed immediately from the scanner. During deep MRI sessions, participants will be monitored at all times by research personnel associated with the project or the investigators themselves. They will be encouraged to contact the study team if they notice any unusual symptoms or untoward side effects. The investigators have extensive prior experience in the utilization of MRI for research. The MRI machine is operated within FDA guidelines so the potential for inducing PNS is low. Women of childbearing potential will be required to take a urine pregnancy prior to MRI. If refused, the participant will be excluded from MRI portion of the protocol.

